The evaluation brief states that the evaluation should 'assess the nature of developments in key areas of performance, such as prescribing patterns'. The proposal recognises this as a worthwhile area, if not major, since it is likely that the most marked impacts of budgets on general medical services (GMS) prescribing will be associated with the cash-limited prescribing budget in standard GP fundholding.

However, interesting developments continue to occur, such as recent evidence that SFH practices are reducing their prescribing costs by buying drugs for their discharged patients from the hospital, thereby reducing cost compared with retail pharmacies while improving pharmaceutical continuity. TPPs may make greater use of these post-discharge drug packages from hospital. Prescribing costs and their control are thus an important issue for GMS generally. Research on the quality of prescribing is handicapped by the widely recognised absence of an adequate measure of volume of prescribing which can be applied at practice level or any adequately defined 'gold standard'. 'Prescribed items' have been shown (Leeds, Prescribing Research Unit) to be weakly correlated with total quantity prescribed and previous fundholding research (Edinburgh, Department of General Practice) using the 'daily defined dose' (DDD) technique has shown this to be a superior approach, affording different insights than previously available. DDDs are not yet available in England, but may be available to be attached to PACT data during 1996. Regrettably, Scottish research cannot be directly translated to English prescribing research because the two systems of handling prescribing data (PACT and SPA) are not computer compatible. The amount of resource which would be needed to solve this problem for the current evaluation is not realistic. However, a number of sensible checks on prescribing issues can be incorporated at relatively little expense, given the support of medical advisors/prescribing advisors. The Audit Commission suggested a number of quality measures or proxies, none are yet of proven value nor known to be workable at practice level. However, there have been promising developments on quality assessment using routine data such as McGavock et al's work in Northern Ireland which will be reviewed and used if deemed appropriate.

Specific questions

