- 1. What is the outturn in terms of cost per patient in relation to GMS prescribing budget and historic patterns of spending in TPP and reference SFH practices?
- 2. What systems have been put in place at TPP practices to monitor and control drug expenditure (eg formularies, drug utilisation review, drug supply from hospitals etc) or to incorporate novel prescribing issues into contracts?
- 3. What is the profile of use of mental illness drugs such as anxiolytics (including hypnotics), antidepressants in general, and SSRIs, specifically, in TPP and reference SFH practices?
- 4. What new awareness of prescribing issues will be introduced into TPP contracts as against SFH contracts?

Overall, it is hypothesised that there will be no difference between TPP and SFH practices in patterns of prescribing.

Questions 1-3 are budgeted for in the resources available under Contract 121/6090. Question 4 can only be addressed with additional resources not currently available, and is not included in the contract to which this protocol refers. However, it has emerged as a consequence of discussions between DH officials and members of the research consortium. A study in this area may be funded as part of a separate contract if it appears that TPPs are making explicit statements about prescribing in their contracts.

Method

The principal comparisons to be made in this component of the evaluation will be, firstly, between all TPP practices and selected reference SFH practices and non-SFH practices in the same health authority area and, secondly, between 'high' and 'low' funded TPP sites and local reference SFH and non-SFH practices. The selection of appropriate local comparison practices for each TPP site will be made by April 1996 on the basis of the findings from the first round of main site visits conducted in autumn/winter 1995.

During the first site visits (see section 4, above), the interviewer will obtain information about TPP measures to reduce prescribing costs or to incorporate novel prescribing issues into contracts. The feasibility of obtaining the equivalent of PACT level 3 data on BNF chapter 4 from 1 April 1995 for all TPP practices and local SFH practices will also be determined.

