'Prescribing amounts' and statistics for cost per patient in TPP, SFH and non-FH practices will be requested from local medical or prescribing advisers. The levels of prescribing budgets set in 1995-96, 1996-97 and 1997-98 will be calculated and tabulated on a per patient basis along with prescribing expenditure. Item counts will be recorded, but are unlikely to be of great use.

In order to answer the third question posed above on the use of mental illness drugs such as anxiolytics and antidepressants, especially SSRIs, the DDD method will be used. The prescribing of psychotropics is of particular interest because both TPP practices and SFH practices are involved in purchasing mental health services. Previous work has suggested that DDDs prescribed for SSRIs in absolute terms and as a proportion of all antidepressants may be different in SFH and non-SFH practices. In order to obtain a general picture of how TPP sites approach psychotropic prescribing, contracts for mental health services negotiated by TPP sites and their host health authority will be obtained as part of the 'core' evaluation and content analysed in Edinburgh for remarks and stipulations concerning psychotropic prescribing. This part of the evaluation will be closely integrated with the service-specific study on services for people with serious mental health problems led by [name] and subject of a separate, but related proposal.

This will be followed by an analysis based on DDDs of the prescribing of anxiolytics and antidepressants (BNF 4.1 and 4.3, equivalent to PACT level 3) using the method previously reported by the Edinburgh team (BMJ 309: 705-10). Samples of six 'high' and six 'low' prescribing budget TPP sites and twelve local reference SFH practices will be randomly selected to provide 10,000 TPP patients and 10,000 SFH patients. Prescribing data will be obtained from the local FHSAs.

It may be desirable, if time allows, to repeat this analysis for H₂ antagonists as well as SSRIs. Advice on data analysis and interpretation for this part of the study will be available from the Leeds Prescribing Research Unit ([name]).

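### Hospital-supplied discharge drugs are not quantified in the prescribing cost comparison, so an unequal change of supplier could be read as an effect of total purchasing

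*Protocol*

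**What the plan says.** The Introduction to section 5.3 says that "SFH practices are reducing their prescribing costs by buying drugs for their discharged patients from the hospital", and that "TPPs may make greater use of these post-discharge drug packages from hospital".

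Question 1 under Specific questions is: "What is the outturn in terms of cost per patient in relation to GMS prescribing budget and historic patterns of spending", for TPP and reference SFH practices. The section's main comparison also takes in non-fundholding (non-FH) practices and is before-and-after. Under Method, "statistics for cost per patient in TPP, SFH and non-FH practices will be requested from local medical or prescribing advisers". Question 3 is answered by "an analysis based on DDDs of the prescribing of anxiolytics and antidepressants (BNF 4.1 and 4.3, equivalent to PACT level 3"), for which "Prescribing data will be obtained from the local FHSAs". Table 8.1 names PACT/SPA as the data system for the component.

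Hospital supply of drugs appears in three further places:

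- Question 2 lists it as an example of the systems TPP practices may use to control drug spending.
- Item G4 of the lead-GP interview guide (Annexe 1) asks TPP respondents about local ways of reducing prescribing costs. It asks for no date, quantity or value.
- Question 4 would examine what contracts require about drugs given to discharged patients. Section 5.3 places it outside the present contract for want of funds, and it would describe contract terms, not quantities.

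**The concern.** The Protocol names a route by which drug supply can move from retail pharmacy to hospital, and then measures cost against a budget that may not contain the hospital part. Nothing in section 5.3 says whether hospital-bought packs are inside the routine figures. Nothing plans to size them, and the reference practices are not asked about them at all.

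If packs fall outside the figures and one group uses them more, that group's recorded cost per patient falls while its patients receive the same drugs. The evaluation could then credit total purchasing with lower prescribing cost when much of the difference is a change of supplier. This is a matter of what is asked of sites and advisers, so later analysis cannot repair it if the question was never put.

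**Working it through.** Section 5.3 gives no expected difference, variance or power for cost per patient, and no figure for pack use, so there is no planned number to reproduce. What follows is an illustration.

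**Taken from the Protocol:** SFH practices already use packs; TPPs may use them more; packs cost less than retail supply; the cost measure is GMS outturn.

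**Assumed (the Protocol gives no values):**

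- Packs are absent from the GMS figures.
- Patients' true drug use is the same in both groups.
- *h* is the share of drug spend, at retail prices, that is moved to packs (*h*T for TPPs, *h*R for the reference group).
- *r* is the pack price as a fraction of retail.

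**Step 1: recorded difference.** Recorded cost is proportional to 1 − *h*, so the recorded TPP-versus-reference difference is (1 − *h*T)/(1 − *h*R) − 1.

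| *h*T | *h*R | Recorded difference |
|---|---|---|
| 2% | 0% | −2.0% |
| 5% | 0% | −5.0% |
| 10% | 0% | −10.0% |
| 5% | 2% | 0.95/0.98 − 1 = −3.1% |
| 10% | 5% | 0.90/0.95 − 1 = −5.3% |
| 5% | 5% | 0% |

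**Step 2: how much of it is real.** True cost is proportional to 1 − *h*(1 − *r*). With *h*R = 0, the recorded saving is *h*T, the true saving is *h*T(1 − *r*), and the overstatement is *h*T × *r*. For *h*T = 5%:

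| *r* | Recorded saving | True saving | Overstatement |
|---|---|---|---|
| 0.5 | 5% | 2.5% | 2.5 points |
| 0.7 | 5% | 1.5% | 3.5 points |
| 0.9 | 5% | 0.5% | 4.5 points |

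**Step 3: which contrast is most exposed.** Take *h*T = 5% and *r* = 0.7.

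- Against SFH practices at 2%, the recorded difference is −3.1%. The true difference is (1 − 0.05 × 0.3)/(1 − 0.02 × 0.3) − 1 = 0.985/0.994 − 1 = −0.9%, so the overstatement is about 2.2 points.
- Against non-FH practices, if these use no packs, it is 3.5 points.
- A before-and-after reading within TPPs carries the whole shift made over the period. A comparison with SFH practices cancels whatever part is common to both.

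**Step 4: when it vanishes.** If packs are in the figures, or *h*T = *h*R, the bias is zero.

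**The case against.** The strongest reply is that the central premise is not in the documents. No section says that packs leave the GMS or FHSA record. The statement that SFH practices reduce their prescribing costs this way also fits a cheaper pack that is still counted as a prescribing cost. This stands, and it makes the concern conditional.

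Second, a reader might infer that the Protocol predicts the shift. It does not: it says TPPs may make greater use of packs, and its only stated hypothesis is no TPP–SFH difference in prescribing patterns. Since SFH practices already use packs, only unequal use biases that contrast. There are grounds to think use could be unequal: the footnote to Table 5.1 calls emergency admissions the largest addition over standard fundholding, so TPPs purchase for more discharges. That makes a differential plausible, not shown.

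Third, analysts would not be blind to the issue. Question 2 is funded, site visits ask about cost-reducing measures, and TPP contracts are gathered in the core evaluation (section 4). All this would alert them at TPP sites. It would not size the effect, and it says little about reference practices.

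Fourth, moving supply is a real effect on GMS outturn, and part of the fall is a true saving, since the Protocol describes "buying drugs for their discharged patients from the hospital, thereby reducing cost compared with retail pharmacies". This also stands; it limits the error to the part *h* × *r*.

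Finally, the dose-based (DDD) analysis covers anxiolytics and antidepressants only. The discharge areas listed for question 4 are A&E, early surgical discharge and day surgery, and mental health contracts will be content analysed for psychotropic prescribing terms. No section ties packs to these drugs.

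**Conclusion.** The point holds in a limited and conditional form. Section 5.3 identifies hospital supply as a cost-reducing route, measures cost against the GMS budget, does not say whether that measure includes hospital packs, and collects nothing quantitative on them in any group. If packs are excluded and their use is unequal, recorded cost differences overstate the saving. On the assumed values above the overstatement is 2.5 to 4.5 percentage points for a 5% shift against practices using none, and about 2 points against SFH practices with 2% shifted and packs at 0.7 of retail. The non-FH and before-and-after contrasts are more exposed than TPP versus SFH.

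Two stronger readings are not supported. One is that savings would be overstated several-fold: the ratio of recorded to true saving is 1/(1 − *r*), which is 5 at an assumed *r* of 0.8 however small the shift. For a 2% shift at that price the error is 2.0 − 0.4 = 1.6 points. The other is that psychotropic DDDs are biased in the same way: the link to packs is not shown, and a caveat is enough there. This is a cheap improvement to a component that the Protocol itself treats as secondary.

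**What to change.** 1. In the requests already going to prescribing advisers, and in the planned TPP interviews, establish whether the cost and FHSA figures include hospital-supplied discharge drugs.
2. Record for TPP, SFH and non-FH practices alike whether such supply is used, from what date and, where available, its annual value. For the reference practices this should go through the advisers, because the telephone interviews that would have reached the SFH references belong to the unfunded question 4.
3. Report cost per patient as GMS outturn alone, and again with pack costs added where known or with pack-using practices left out.
4. Limit conclusions from GMS or FHSA data to recorded GMS prescribing.
5. For psychotropic DDDs, add a caveat or one sensitivity analysis without pack-using practices.

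The cost is one or two extra items in contacts already planned and one extra tabulation. The downside is that pack values will be incomplete at some practices: the Protocol does not say that advisers hold hospital contract values, and for non-FH practices the health authority is the purchaser (section 6, Models of Purchasing). Where values are missing, the exclusion analysis and the limited conclusion still apply. The items should be agreed before comparison practices are chosen, which section 5.3 sets for April 1996.

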the factors associated with successful set-up and operation of total purchasing;

the costs and effectiveness of total purchasing compared with health authority purchasing in the context of ordinary GP fundholding (SFH);

the benefits to patients of total purchasing compared with health authority purchasing in the context of SFH;

so that the best models for further development of primary care-led purchasing in the NHS can be developed.

OBJECTIVES

The proposed national evaluation of second wave TPPs is structured to shed light on a number of more detailed research questions which build on previous theoretical and empirical work on the operation of internal or quasi-markets for health services. Robinson and [name] (1994) identify five central goals of the implementation of reforms such as TP against which the success of such schemes can feasibly be evaluated:

quality; efficiency; responsiveness to the concerns of patients; choice of service and/or provider; service provision in relation to need.

Following Bartlett and [name] (1993), they go on to specify five plausible conditions which have to be satisfied for reforms such as TP to stand a good chance of achieving the above goals. The conditions are:

- 1. access to accurate information on activity, the costs and quality of services, especially for purchasers;
- a competitive market structure (except where a natural local monopoly exists on the provider side which needs to be matched by an equally strong local purchaser);
- appropriate motivation on the part of purchasers and providers (ie providers must to some degree be motivated by financial considerations and purchasers by patients' well-being);
- 4. regulation of any incentive for either purchasers or providers to discriminate between patients in favour of those who are least expensive to treat;

5. a reasonable level of transactions costs (ie for any level of additional benefit which TP may create, the administrative costs must be lower than the bureaucratic systems which it replaces).

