The study will focus on the *incremental* costs associated with the change from Model 2 to Model 3, and will consider costs falling on all of the main affected parties: GPs, the DHA/FHSA; and the main acute, community and mental health providers. The way in which the comparison has been framed means that it is not possible to restrict attention solely to the transaction costs borne by general practitioners.

Specific questions

Within the budget set for the study, the extent of comparative information which can be collected is limited. However, it should be possible to address a number of key research questions.

1. What differences exist, if any, in the transaction costs associated with different TP sites? What seem to be the ways of minimising transaction costs?

Some information will be available from the first phase of the 'core' evaluation (involving all sites in England and Scotland - see section 4) to allow a broad taxonomy to be developed of different ways of organising total purchasing, and of differences between sites in terms of level of activity. A comparison of the costs associated with different sites drawn from the taxonomy should provide some insight into the main determinants of differences in cost.

The core evaluation will also provide some limited information on transaction costs for all sites which will strengthen this aspect of the comparison.

2. What are the likely costs to primary care providers (general practice teams) involved in a move from standard fundholding to total purchasing?

This question can be addressed in two ways: i) by means of a before-and-after comparison of pilot sites within the study which were previously standard fundholders; and ii) by a comparison of costs in the TPP site with those in a matched SFH control practice (or group of practices) within the same DHA.

3. What are the additional costs (to GPs, DHA/FHSA and local providers) resulting from the introduction of total purchasing alongside DHA and SFH purchasers?

As a minimum, this question can be addressed by a before-and-after comparison of costs to the DHA/FHSA, GPs themselves and the main local providers. For the DHA/FHSA and providers, a before-and-after design may not be necessary, since they will be dealing currently with both SFHs and TPPs. In this case it should be possible to isolate incremental costs directly.

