If resources are sufficient, it would also be useful to compare the costs to DHA/FHSA and providers in a TPP District with costs in a comparable District without a TPP. This would be a useful control against the possibility that Districts with TPP sites are in some way unrepresentative of Districts as a whole.

To facilitate comparison, the magnitude of transaction costs will be expressed initially as a percentage of total health expenditures. The study will, however, offer an opportunity to test the viability of other possible units of comparison.

Method

Apart from the work of Bevan (1995a, b), which is set very much at a macro level, and one unpublished study commissioned by the NHS Executive, there are no previous studies in the UK which attempt to estimate transaction costs in the NHS (or in health care more generally. See Pitelis (ed), 1993). Developing and testing a suitable methodology is therefore an important objective of this study.

With the exception of the limited amount of information which will be collected as part of the core evaluation covering all of the TPP sites, all of the information relevant to this study will be collected from a sample of sites drawn from the national pilots. Details of the principles of sample selection are outlined below.

Transaction costs arise from functions or activities associated with the need to obtain information, and the need to negotiate, monitor and enforce contracts. The main part of the study will involve a series of semi-structured interviews with key stakeholders in each of the organisations identified above: the TP manager and lead GP in the TPP site; the DHA/FHSA lead; the lead GP in a control SFH practice locally; and representatives of each main local provider (typically the main acute, community and mental health Trusts).

The objective of the interviews will be to identify:

- 1. the range of additional functions or activities associated with total purchasing, and
- 2. the *resources* (in terms of personnel, time and other resources) which are devoted to undertaking these activities and functions.

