Information will be collated and analysed within a structure such as that shown in Figure 6.2, which will also form the basis of a questionnaire to be used in the interviews. In Figure 6.2 the main potential sources of transaction costs are classified into four groups: i) the costs of information; ii) contract-related costs; iii) costs which are activity-related; and iv) the costs associated with coordinating activity within the TPP group and between the TPP and the DHA/FHSA. This is a generalisation of the main sources of transaction costs identified above.

It is in the nature of the questions which need to be addressed in this part of the work that most of the relevant information (for example, about functions and activities) will be qualitative. This will be supplemented with quantitative data on resource use and costs.

Further contact with the TPP site, the DHA/FHSA lead and the main provider organisations will seek to identify:

 the costs of the real resources associated with functions, and with the time and personnel inputs identified in the interview.

It is expected that each site will be visited at least twice: once in each of the two contracting years of the study. Data will be analysed in line with the research questions outlined above.

The use of a diary card in the periods between interviews to record the use of time will be considered. This is a feature of the design of the core evaluation which may usefully be adapted for use in the present study.

In addition, it is intended to attempt a broader (macro) approach to estimating transaction costs by comparing total health expenditure in the sample Districts with some global measure of activity (such as FCEs) in each of the sample years and in the preceding year. Although crude, some global measure of NHS expenditure per FCE (or incremental FCE per £000 of additional budget in each year) will give an indication of the extent to which additional spending is associated with additional activity or additional administration costs

Sample Selection

The size of sample which can be handled within the study is a function of the extent of resources available. The design suggests the need to carry out 6-7 interviews per year for each pilot site included in the sample: even more if a comparison is attempted with a non-TPP District. The need to collect additional cost information will increase the number of potential contacts by a further 50 per cent.

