9. TRANSACTIONS COSTS

What identifiable, direct additional costs has the site incurred so far associated with the decision to become a TP pilot?

How have these costs been met?

Have any existing staff been redeployed from other duties?

How much time has the lead GP and other GPs spent on average each week since the site became a TP pilot on TP-related work?

How have the practices coped with the clinical consequences of having GPs working on TP tasks?

10. GP's PERCEPTIONS OF THE MAIN PROS AND CONS OF TOTAL PURCHASING

Please list these in comparison with being a SFH practice/practitioner.

What appears to be the attitude towards the possibility of adverse selection (cream-skimming)?

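### The transactions-cost interviews are worded to collect what total purchasing adds, and the comparison that would reveal work it removes can be waived, so the increment risks being gross

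*Protocol*

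**What the plan says.** Under Models of Purchasing, section 6 defines the target as the incremental "costs associated with the change from Model 2 to Model 3, and will consider costs falling on all of the main affected parties". Model 2 is purchasing by the DHA and standard fundholders. Model 3 adds total purchasing pilots, which hold part of the DHA's budget by devolution.

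Under Method, the main part of the study is a set of semi-structured interviews with pilot, DHA/FHSA, control-practice and provider respondents. Their first aim is to identify "the range of additional functions or activities associated with total purchasing". Their second is to identify the resources "which are devoted to undertaking these activities and functions". Costs are then attached to the functions, time and staff that the interviews have brought out.

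Under Specific questions, question 3 asks for the extra cost to all parties. It offers a before-and-after comparison for the DHA/FHSA, GPs and providers as the least that can be done. It then says that for the DHA/FHSA and providers "a before-and-after design may not be necessary, since they will be dealing currently with both SFHs and TPPs", and that the increment can be read off directly.

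Condition 5 in section 2 gives the yardstick: for any level of added benefit, "the administrative costs must be lower than the bureaucratic systems which it replaces".

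**The concern.** The target and the instrument do not match. A change from one purchasing model to another can move work in both directions. Once part of the budget is devolved, needs assessment, contracting and monitoring for those patients and services may fall at the DHA while they rise at the pilot. The stated interview aims look in one direction only, and the resource question is tied to the same functions.

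The waiver falls on the bodies where work could be displaced. A DHA officer who now deals with both standard fundholders and a pilot can say how long the pilot takes. Work the officer no longer does is not among those dealings, so it goes unseen unless someone asks what has changed.

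The figure is used elsewhere. Section 6 opens by asking whether transactions costs exceed the gains from total purchasing, and objective 5 of section 5.2 sets efficiency gains against changes in transactions costs. The maternity proposal says its method will mirror this one and also collects additional activities. An increment that counts additions and misses offsets would weigh against total purchasing in each place.

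**Working it through.** The protocol gives no cost figure, effect size or power for this component. It expects that "most of the relevant information (for example, about functions and activities) will be qualitative". There is nothing to reproduce, so the check compares provisions and then applies one identity.

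**1. What each provision can observe at the DHA/FHSA and providers**

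| Provision (section 6) | Can it show work reduced or ended? | Status |
|---|---|---|
| Interview aims (Method) | Not as worded: additional functions and their resources | Firm |
| Costing step (Method) | Only for what the interviews identify | Firm |
| Direct isolation from concurrent dealings (question 3) | No | Offered in place of before-and-after |
| Before-and-after comparison of costs (question 3) | Yes | Waivable for the DHA/FHSA and providers |
| Districts without pilots (section heading; question 3; Sample Selection) | Yes, as a contrast between districts | Called the main comparison in the heading; elsewhere only if resources allow, in year two, with around 3-4 representatives in four districts |
| Spending against a global activity measure (Method) | In principle, but total spending does not isolate administration | Described as crude |
| Before-and-after and matched-practice comparison (question 2) | For general practice teams only | Offered |

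The firm rows look at additions. The rows that would give a net figure for the DHA/FHSA and providers are waivable, conditional or too coarse. The stated purpose of the control districts is to guard against pilot districts being unrepresentative, not to measure offsets.

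**2. Direction of the error**

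Let A be the cost of functions added and S the cost of functions reduced or ended, over all parties.

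- Target: net increment = A - S.
- Additions-only tally: A.
- Error: A - (A - S) = S, which is zero if nothing is displaced and upward otherwise.
- With d = S/A, reported/net = A/(A - S) = 1/(1 - d).

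**3. Illustration only**

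The protocol gives no value for d, so these are assumed values across a range:

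- d = 0: 1/(1 - 0) = 1.00, no overstatement.
- d = 0.25: 1/0.75 = 1.33.
- d = 0.50: 1/0.50 = 2.00.
- d = 1: the true net is zero, and A is reported.
- d above 1: the true net is a saving, reported as a cost.

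None of these is a forecast.

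**The case against.** The best case against the point is that section 6 does not confine itself to additions. It names a before-and-after comparison covering the DHA/FHSA and providers, and the waiver is permissive, not a decision. Figure 6.2, the basis of the questionnaire, lists purchaser and provider functions in general terms, and semi-structured interviews may bring out work that has stopped. Sites are visited in two contracting years. This stands in part: a team following section 6 could arrive at a net figure. But nothing makes it do so, and the stated interview aims and the waiver both point the other way.

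The second argument is that displacement may be small. The DHA remains finally answerable for the devolved budget and gains a new accountability link. Figure 6.1 keeps the DHA-provider relationship in Model 3, and section 2 describes the pilots as considerably smaller than their DHAs. This stands in full as a limit on size.

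Two stronger readings are tempting. A reader might infer that removed work is never recorded and that the result is certain to be overstated. The protocol does not support that, because net designs are present and displacement is not established. A reader might also cite Annexe 4, which asks "What identifiable, direct additional costs has the site incurred so far associated with the decision to become a TP pilot". But that annexe guides the write-up of core-evaluation interviews with lead GPs. It is not the section 6 instrument, and its transactions-costs section also asks about redeployed staff. The point does not rest on it.

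**Conclusion.** The point holds as a risk created by the wording. Section 6 targets a net change across all parties, states an additions-only aim for its main data source, and allows the DHA/FHSA and provider comparison to be replaced by a method that cannot observe reduced or ended work. The remaining net comparisons do not reliably fill the gap.

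Any resulting bias is upward. Its size equals the cost of displaced DHA and provider work that goes unrecorded; it cannot be derived from the protocol and may be close to zero. The conclusion assumes that the interviews follow their stated aims, that the waiver is used, and that the control-district work is not done or is too thin to capture the offset. If the before-and-after comparison were kept for total DHA/FHSA and provider costs, the problem would largely disappear.

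**What to change.** 1. In section 6, Method, and in the Figure 6.2 questionnaire, widen the interview aim to functions added, increased, reduced, transferred or ceased because of total purchasing. Ask each party for the time involved in each direction.
2. In question 3, delete the statement that before-and-after may be unnecessary for the DHA/FHSA and providers. Use the visits already planned in each of the two contracting years, at the four sample sites, to compare their time on the devolved services before and after devolution. Section 2 says the vast majority of sites start purchasing in April 1996 with 1995/6 as preparation, so a visit in that year would give a baseline at those sites. Where a site went live early, the baseline would rest on recall.
3. Report the net increment, with gross additions shown separately.

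The cost is slightly longer interviews and some recall error about tasks that have stopped. The component has only a half-time research fellow, but no new sites, visits or control districts are required. A before-and-after change in time can have other causes, so the questions should stay tied to changes that respondents attribute to total purchasing. If displacement proves to be nil, the net and gross figures will agree and the estimate will be easier to defend.
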